#### 4.3.2. Key Secondary Endpoint

With 157 patients enrolled, the study will have a minimum detectable difference (i.e., 50% power) between the two treatment groups in change from baseline in eGFR of approximately 2.9 mL/min/1.73 m^2, and 80% power to detect a difference of 4.0 mL/min/1.73 m^2 for the key secondary endpoint at Year 1 and at Year 2. The power calculation, which was based on a 2-sample t-test as an estimate for the planned ANCOVA analysis, assumes the following:

- Two-sided Type I error rate of 0.025 for Year 1 and 0.025 for Year 2
- Standard deviation of change from baseline in eGFR of 8 mL/min/1.73 m^2
- Multiple imputation is used for missing data
- Analyses of the key secondary endpoint are based on the ITT population

#### **4.4. Randomization**

Patients enrolled in the Phase 3 cohort are randomized 1:1 to either bardoxolone methyl (BARD) or placebo. Randomization is stratified by screening ACR ( $\leq 300$ ,  $> 300$  to 1000, and 1000 to 3500). Patients with macroalbuminuria ( $300 \text{ mg/g} < \text{ACR} \leq 3500 \text{ mg/g}$ ) at the Screen B visit do not comprise more than approximately 40% of patients enrolled in the Phase 3 cohort.

Randomization is generated using a centralized Interactive Web Response System (IWRS).

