**Diagnosis and main criteria for inclusion (see protocol section 8.1):**

1. Male and female patients  $12 \leq \text{age} \leq 70$  upon study consent;
2. Diagnosis of Alport syndrome by genetic testing (documented mutation in a gene associated with Alport syndrome, including COL4A3, COL4A4, or COL4A5) or histologic assessment using electron microscopy;
3. Screening eGFR (average of Screen A and Screen B eGFR values)  $\geq 30$  and  $\leq 90$  mL/min/1.73 m^2. The two eGFR values collected at Screen A and Screen B visits used to determine eligibility must have a percent difference  $\leq 25\%$ ;
4. Albumin to creatinine ratio (ACR)  $\leq 3500$  mg/g at Screen B visit. Up to 50% of patients in the Phase 2 cohort and approximately 40% of patients enrolled in the Phase 3 cohort can have ACR of 301 to 3500 mg/g. Once enrollment of these patients is complete, the ACR inclusion criterion is  $\leq 300$  mg/g;
5. Patients receiving an angiotensin-converting enzyme (ACE) inhibitor and/or an angiotensin II receptor blocker (ARB) should be receiving the maximally tolerated labeled daily dose (MTLDD), for at least 6 weeks prior to the Screen A visit. The dosage of ACE inhibitor and/or ARB should remain the same throughout the remainder of the study (i.e., no change in dosage or medication), and any potential changes should be discussed with the medical monitor. Patients not currently taking an ACE inhibitor and/or ARB because they are not indicated or because of a medical contraindication may be eligible provided the patient has not taken an ACE inhibitor and/or ARB at least 8 weeks prior to the Screen A visit (these patients must be discussed with the medical monitor prior to enrollment);

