### **6.4.4. Urine Albumin to Creatinine Ratio**

Baseline ACR is defined as the last ACR value prior to the first study drug administration. Baseline ACR is summarized using the geometric mean of ACR values.

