### 6.5.6.1. Prognosis of CKD by eGFR and Albuminuria Category

Prognosis of CKD is determined by the intersection of the following eGFR and albuminuria categories (KDIGO 2012):

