**Table 8. Model Parameter Abbreviations**

Abbreviation	Model Term
ACR_STRAT	ACR strata used in randomization
BASE_eGFR	Baseline eGFR
BASE_eGFR x VISIT	the interaction between baseline eGFR and time
TRT	treatment group
TRT_EXP1_	fraction of one-year exposure to treatment (Section 6.5.11)
TRT_EXP2	fraction of two-year exposure to treatment (Section 6.5.11)
TRT x VISIT	the interaction between treatment and time
VISIT	analysis visit used as time

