### **8.6.1. Primary Analysis of the Year 1 Primary Efficacy Endpoint**

The Year 1 primary endpoint of this study is the change in eGFR at Week 48 (i.e., the end of the first year of drug exposure). The change from baseline eGFR for patients treated with bardoxolone methyl is compared with placebo at Week 48 using mixed models repeated measures (MMRM) analysis, with baseline eGFR (BASE\_eGFR), ACR strata (ACR\_STRAT), and fraction of one-year exposure to treatment (TRT\_EXP1) as covariates and the following fixed factors: treatment group (TRT), time (i.e., VISIT; analysis visit number), the interaction between treatment and time (TRT x VISIT), and the interaction between baseline eGFR and time (BASE\_eGFR x VISIT) as covariates. Inclusion of the fraction of expected one-year exposure to treatment (Section 6.5.11) in the MMRM model as a covariate provides an adjustment for eGFR values collected from early discontinuation patients having less than 1-year of drug exposure.

The trial design separates discontinuation of study drug from discontinuation of study follow-up. Therefore, patients may discontinue early from study drug while continuing follow-up with study visits and assessments. The primary analysis of eGFR at Week 48 uses available eGFR values irrespective of whether or not a patient is receiving treatment. The MMRM analysis uses all eGFR values collected through Week 48 according to analysis visits 0, 1, 2, 4, 6, 8, 12, 24, 36, and 48 (Section 6.5.4). An unstructured covariance matrix is used.

In the event the MMRM model with an unstructured covariance structure does not converge, the following covariance structures are substituted, in the order listed. Each subsequent covariance structure is used only if each previous covariance structure is used and no previous model converged.

1. Heterogeneous Toeplitz covariance structure (assuming different variances at each time point and that measurements taken closer together in time are more highly correlated than those taken farther apart).
2. Toeplitz covariance structure (assuming measurements taken closer together in time are more highly correlated than those taken farther apart).
3. First order auto-regressive [AR(1)] covariance structure (assuming measurements taken closer together in time are more highly correlated than those taken farther apart, but the correlation is more constrained than the Toeplitz structure).

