### **8.7. Year 1: Key Secondary Endpoint**

#### **8.7.1. Primary Analysis of Year 1 Key Secondary Endpoint**

The Year 1 key secondary endpoint of this study is the change in eGFR at Week 52 (i.e., 4 weeks following the last dose after one year of drug exposure). Analysis of Week 52 assesses the preserved drug benefit (relative to placebo) following withdrawal of treatment; therefore, analysis of Week 52 data does not include the eGFR values collected during treatment.

The change from baseline eGFR at Week 52 for patients treated with bardoxolone methyl is compared to placebo using an analysis of covariance (ANCOVA) model, with BASE\_eGFR,

ACR\_STRAT, and TRT\_EXP1 as covariates, and TRT as the fixed effect. Inclusion of the fraction of expected one-year exposure to treatment (TRT\_EXP1; Section 6.5.11) in the ANCOVA model as a covariate provides an adjustment for eGFR values collected from early discontinuation patients having follow-up collected after less than 1-year of drug exposure.

The ANCOVA analysis uses eGFR values collected in the Week 52 analysis window (Section 6.5.4), which includes the follow-up assessment for patients who discontinued treatment early in the first year. Missing Week 52 eGFR data are imputed as defined in Section 8.5.3 using standard imputation.

The difference between bardoxolone methyl and placebo in change from baseline of eGFR is estimated along with the 95% confidence interval at Week 52.

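### The four confirmatory eGFR models adjust for albuminuria only through three randomisation strata; adding continuous baseline ACR would give a modest gain in precision

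*SAP*

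**What the plan says.** SAP Section 4.4: "Randomization is stratified by screening ACR", in three levels cut at 300 and 1000 mg/g. Patients above 300 mg/g "do not comprise more than approximately 40% of patients enrolled in the Phase 3 cohort". Inclusion criterion 4 in the Technical Summary Report repeats the cap: "approximately 40% of patients enrolled in the Phase 3 cohort can have ACR of 301 to 3500 mg/g".

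Table 8 defines the model term ACR_STRAT as "ACR strata used in randomization", and Section 6.5.7.2 lists the same three levels. It is the only albuminuria term in the confirmatory models:

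- Week 48 (8.6.1) is compared "using mixed models repeated measures (MMRM) analysis, with baseline eGFR", ACR_STRAT and the exposure fraction, plus treatment, visit, and the interactions of treatment and of baseline eGFR with visit.
- Week 52 (8.7.1) is "compared to placebo using an analysis of covariance (ANCOVA) model" with baseline eGFR, ACR_STRAT, exposure fraction and treatment.
- Weeks 100 and 104 (8.8.1, 8.9.1) take over these models with the two-year exposure fraction, and the Week 100 model adds the later visits. The SAP addendum corrects that fraction (3.1) and adds region (4.4.2). It adds no ACR term.

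A finer variable exists. Section 6.4.4: "Baseline ACR is defined as the last ACR value prior to the first study drug administration". Section 6.5.7 log-transforms ACR and has a rule for results below the detection limit. Section 6.5.6.1 says "Prognosis of CKD is determined by the intersection of the following eGFR and albuminuria categories", and Table 6 splits the range up to 300 mg/g at 30 mg/g.

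**The concern.** A covariate that predicts eGFR change narrows the treatment contrast. Here the albuminuria covariate is coarsest where most patients are: everyone at or below 300 mg/g gets the same adjustment, although the SAP's own CKD categories divide that range in two. Stratified randomisation does not balance ACR inside a stratum, and the model cannot correct a chance imbalance there.

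What is at stake is some precision in the confirmatory contrasts. It is calculable only for the key secondary ANCOVA, which is planned at about 80% power with two-sided alpha 0.025. Section 2.1 calls the off-treatment change the main analytical intent of the trial.

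**Working it through.** **1. Share in the lowest stratum.** 100% − 40% = 60%; 0.60 × 157 = 94.2, so at least about 94 patients. The cap is approximate.

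**2. The plan's own figure (4.3.2).** SD 8, 78 and 79 patients, two-sided alpha 0.025, two-sample t-test.

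- SE = 8 × √(1/78 + 1/79) = 1.277.
- Smallest significant difference = 2.263 × 1.277 = 2.89 (SAP: 2.9).
- Noncentral-t power at a difference of 4.0, with 155 df, is 80.7% (SAP: 80%).

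The planning figures reproduce.

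**3. Gain from within-stratum ACR, first route.** These inputs are assumptions and are not in the documents: eGFR change lower by b per 10-fold ACR; SD of log10 ACR equal to s within the ≤300 stratum and 0.155 within each upper stratum; 60% of patients at ≤300.

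Variance share v = [0.6(b·s)² + 0.4(b·0.155)²] / 64. Equivalent extra patients = 157·v/(1 − v). Power uses SD 8·√(1 − v).

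| b | s | v | Extra patients | Power at 4.0 |
|---|---|---|---|---|
| 2 | 0.43 | 0.482/64 = 0.75% | 1 | 81.0% |
| 3.5 | 0.50 | 1.955/64 = 3.1% | 5 | 82.0% |
| 5 | 0.58 | 5.286/64 = 8.3% | 14 | 84.2% |

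The same inputs give the typical chance shift of the contrast from within-stratum ACR imbalance, √(64v) × √(1/78 + 1/79): 0.11, 0.22 and 0.37 mL/min/1.73 m². This is the same gain seen another way, not an addition to it.

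**4. Second route.** Assume ln(ACR) is normal, truncated at 3500 mg/g, with 60–70% of patients at or below 300 and log-SD 1.2–2.4. The strata then leave a share w of 30–43% of the ln(ACR) variance unexplained. For a correlation r between ln(ACR) and eGFR change, partial R² = r²w / [1 − r²(1 − w)]. With r = 0.1 and w = 0.303 this is 0.3%; with r = 0.4 and w = 0.433 it is 7.6%. Power at 4.0 is then about 81% to 84%.

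**5. What ACR_STRAT already gains.** The 80.7% in step 2 contains no covariates, so it is not the SAP's model. Keep the slopes of step 3 and assume stratum means of log10 ACR of 1.5–1.9, 2.74 and 3.27 with a 60/20/20 split. The between-stratum variance of log10 ACR is then 0.572 (lowest mean 1.5) or 0.321 (lowest mean 1.9). Multiplying by b²/64 gives the share that the strata remove.

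| b | Removed by strata | Power with ACR_STRAT | Added by ln(ACR) |
|---|---|---|---|
| 2 | 2.0–3.6% | 81.5–82.2% | 0.3 points |
| 3.5 | 6.1–10.9% | 83.3–85.3% | 1.3 points |
| 5 | 12.5–22.3% | 86.0–90.0% | 3.1–3.4 points |

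If SD 8 is read as the total SD, v in the top case becomes 9.4–10.6% of the variance the strata leave. The power gain is as shown in the table.

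**6. Cost if ACR explains nothing.** Dropping from 155 to 154 df at SD 8 lowers power by less than 0.01 points.

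None of this carries over to the MMRM at Weeks 48 and 100. There the gain depends on the ACR slope at that visit and on whether the term is crossed with visit.

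**The case against.** The strongest reply is that nothing here is wrong. Adjusting for the randomisation factor and the baseline outcome is sound, and 300 mg/g is also the boundary that decides the dose ceiling (4.1), so the cut is not arbitrary. That stands: the documents support a refinement, not a defect.

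The size is assumed throughout. The slope that matters is net of baseline eGFR, exposure fraction and, in Year 2, region, all already modelled. The CKD categories in 6.5.6.1 are listed for baseline tables (7.4); they do not show that ACR below 30 versus 30 to 300 mg/g predicts eGFR change once baseline eGFR is known. Baseline ACR is one spot-urine value, and results imputed below the detection limit fall inside the ≤300 stratum, so noise and non-linearity may weaken a linear ln(ACR) term. All of this stands and pulls towards the lower end of the range.

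Three stronger readings are tempting but unsupported:

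- A reader might take 80.7% to 84.2% as before and after for this plan. It is not, because 80.7% omits the stratum term (step 5).
- A reader might conclude that baseline ACR is unused in the trial. It feeds subgroups (8.3), baseline tables (7.4), exposure by ACR (10.2) and ACR summaries (10.5.1). It is absent only from the eGFR models.
- A reader might think a pre-dose covariate carries no bias risk whenever it is added. The covariate itself does not bias the contrast, but its selection can. Under 5.1 the sponsor unblinds if both Year 1 endpoints succeed, 5.1.1 makes Year 1 results final, and 4.3 says the two years are not independent hypothesis sets. A Year 2 covariate chosen after sight of Year 1 data would be open to question.

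**Conclusion.** The point holds as a modest efficiency gain on a valid model. All four confirmatory models adjust for albuminuria only by stratum, and at least about 60% of patients have no albuminuria adjustment within their level.

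Adding ln(baseline ACR) would remove roughly 0.3% to 8% of residual variance, with the planning SD of 8 read as the residual SD. For the key secondary ANCOVA that is about 0 to 3.5 power points beyond what ACR_STRAT already gains, and about 1.3 points at mid-range. The 60% share and the planning power come from the documents. The slopes, spreads, stratum means and correlations are assumptions. No gain is quantified for Weeks 48 and 100.

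**What to change.** Add ln(baseline ACR), as defined in 6.4.4 and with the below-detection rule of 6.5.7, as a continuous covariate beside ACR_STRAT in the Week 100 and Week 104 models (8.8.1, 8.9.1). For the MMRM, state whether it is crossed with visit. Make the same change at Weeks 48 and 52 (8.6.1, 8.7.1) only if Year 1 is not yet unblinded.

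Specify the change before the Year 2 lock, by staff without access to treatment assignments. If those who decide have already seen unblinded Year 1 data, keep the current primary models and make the adjusted version a prespecified sensitivity analysis.

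The cost is SAP wording and, as a main effect, one model degree of freedom, with some dependence on a single spot-urine value. No new data are needed: Screen B ACR is an eligibility criterion, so every eligible patient should have a pre-dose value.

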#### **4.5. Clinical Assessments**

All patients in the study follow the same visit and assessment schedule for the 2 years of total follow-up. [Table 2](#) lists the overall schedule of assessments for the study. Following the first dose of study drug on Day 1, patients are scheduled for in-person assessments during Year 1 of treatment at Weeks 1, 2, 4, 6, 8, 12, 24, 36, and 48, as well as by telephone contact on Days 3, 10, 21, 31, 38, and 45. Patients temporarily discontinue study treatment at Week 48 and are assessed at an in-person Year 1 follow-up visit at Week 52 (4 weeks after the last dose). Patients are dispensed treatment at the end of their Week 52 visit at the same dose level (or matching placebo) as the last dose at Week 48. Patients are assessed for in-person assessments during Year 2 of treatment Weeks 64, 76, 88, and 100. Patients are assessed at an in-person, Year 2 follow-up visit at Week 104 (4 weeks after the last dose).

Assessment	Screen A a	Screen B b	Day 1 c	Wk 1 (Phone) Day 3±2	Wk 1 Day 7±3	Wk 2 (Phone) Day 10±2	Wk 2 Day 14±3	Wk 3 (Phone) Day 21±2	Wk 4 Day 28±3	Wk 4 (Phone) Day 31±2	Wk 5 (Phone) Day 38±2	Wk 6 Day 42±3	Wk 7 (Phone) Day 45±2	Wk 8 Day 50±3	Wk 12 Day 84±3
Informed consent	X														
Inclusion/ exclusion	X		X d												
Demographics and baseline disease characteristics	X														
Concomitant medications	X	X	X	X	X	X	X	X	X	X	X	X	X	X	X
Medical history	X														
Height	X		X	X	X	X	X	X	X	X	X	X	X	X	X
Weight in clinic	X		X	X	X	X	X	X	X	X	X	X	X	X	X
Weight at home			X	X	X	X	X	X	X	X	X	X	X	X	X
Dispense weight diary			X	X	X	X	X	X	X	X	X	X	X	X	X
Collect/review weight diary				X	X	X	X	X	X	X	X	X	X	X	X
ECG	X														
Echocardiogram e	X														
Vital sign measurements	X		X	X	X	X	X	X	X	X	X	X	X	X	X
Physical exam	X		X	X	X	X	X	X	X	X	X	X	X	X	X
Pregnancy test for WOCBP f	X	X	X	X	X	X	X	X	X	X	X	X	X	X	X
Study drug administration															
Dispense study drug			X				X		X			X		X	X
Collect study drug							X		X			X		X	X
Telephone contact				X		X		X		X	X		X		
Adverse event collection			X g	X	X	X	X	X	X	X	X	X	X	X	X
Genetic testing h	X														
Clinical chemistry (incl. eGFR)	X	X	X	X	X	X	X	X	X	X	X	X	X	X	X
BNP and NT-proBNP	X		X	X	X	X	X	X	X	X	X	X	X	X	X
IGF-1 and serum ketones	X		X	X	X	X	X	X	X	X	X	X	X	X	X
Hemoglobin A1c	X														
Hematology	X		X	X	X	X	X	X	X	X	X	X	X	X	X
Urinalysis and microscopy	X		X	X	X	X	X	X	X	X	X	X	X	X	X
Urine collection for ACR i		X													
Visual acuity			X												
Audiology assessment			X												
PGIC															
CGI-I															
Virus serology	X														
PK samples j															X

Assessment	Wk 24 Day 168±3	Wk 36 Day 252±3	Wk 48 Day 336±3	Wk 52 Day 364-6	Wk 64 Day 448±5	Wk 76 Day 532±5	Wk 88 Day 616±5	Wk 100 or End of Treatment k Day 700±3	Wk 104 or Follow-up k Day 728-6
Informed consent									
Inclusion/ exclusion									
Demographics and baseline disease characteristics									
Concomitant medications	X	X	X	X	X	X	X	X	X
Medical history									
Height	X	X	X	X	X	X	X	X	X
Weight in clinic	X	X	X	X	X	X	X	X	X
Weight at home	X	X	X	X	X	X	X	X	X
Dispense weight diary	X	X	X	X	X	X	X	X	X
Collect/review weight diary	X	X	X	X	X	X	X	X	X
ECG			X	X				X	X
Echocardiogram 									
Vital sign measurements	X	X	X	X	X	X	X	X	X
Physical exam	X	X	X	X	X	X	X	X	X
Pregnancy test for WOCB pf	X	X	X	X	X	X	X	X	X
Study drug administration									
Dispense study drug	X	X		X	X	X	X	X	
Collect study drug	X	X	X		X	X	X	X	
Telephone contact									
Adverse event collection	X	X	X	X	X	X	X	X	X
Genetic testing 									
Clinical chemistry (incl. eGFR)	X	X	X	X	X	X	X	X	X
BNP and NT-proBNP	X	X	X	X	X	X	X	X	X
IGF-1 and serum ketones	X	X	X	X	X	X	X	X	X
Hemoglobin A1c			X					X	
Hematology	X	X	X	X	X	X	X	X	X
Urinalysis and microscopy	X	X	X	X	X	X	X	X	X
Urine collection for ACR 	X	X	X	X	X	X	X	X	X
Visual acuity			X					X	
Audiology assessment			X					X	
PGIC	X		X		X			X	X
CGI-I	X		X		X			X	X
Virus serology									
PK samples 									

- a Total Screening period should not exceed 6 months.
  - b Screen B visit should be no more than 30 days prior to Day 1.
  - c Day 1 is the day of administration of the first dose. **On Day 1, all procedures should be performed before study drug administration.**
  - d Screening eligibility procedures do not need to be repeated on Day 1; however, a review of any changes in eligibility criteria should be evaluated prior to Day 1 procedures, and a urine pregnancy test should be performed for WOCBP.
  - e An echocardiogram performed at the Screen A visit or within 6 months prior to Day 1 may be used to determine eligibility.
  - f A serum pregnancy test is performed at the Screen A visit for WOCBP or at any point in time if a pregnancy is suspected. All other pregnancy assessments are urine pregnancy tests. Additional pregnancy assessments are performed more frequently if required by local law or requested by local regulatory authorities or IRBs/IECs.
  - g AE assessments on Day 1 should be performed following study drug administration.
  - h Patients with definitive diagnosis of Alport syndrome from previous genetic testing will not have genetic testing performed as part of the study, but must provide documentation of genetic diagnosis for eligibility.
  - i Albumin to creatinine ratio is measured by first morning void spot urine collection. Appropriate containers for the collection are provided to the patient at the visit prior to collection.
  - j Patients must be instructed to not take their study drug prior to coming to the clinic for visits when PK samples are collected. Patients must administer the study drug dose in the clinic on PK sample collection visits after the 0 hour PK blood sample is collected. Patients will have blood samples for PK analysis drawn just prior to (0 hour) and after (2 and 4 hours) dose administration.
  - k Patients who terminate from the study prior to the Week 100 study visit should be brought back to the clinic as soon as possible for early termination assessments (i.e., end-of-treatment visit) as well as a follow-up visit 4 weeks later.
- Abbreviations: ECG = electrocardiogram, PK = pharmacokinetic, WOCBP = women of child-bearing potential

## 5. PLANNED ANALYSES

The trial design includes hypothesis tests following one and two years of treatment. All available study data are analyzed (1) when Year 1 data are complete, and (2) when Year 2 data are complete. Details of the database lock plans and blinding are described in the Interim Database Deliverable Plan. The strategy for protecting the overall type I error rate of 0.05 for the primary and key secondary endpoints at Year 1 and Year 2 is described in Section 8.4.

A Data Access Plan describes how the sponsor plans to control access to unblinded data following the Year 1 analysis. In the period between the Year 1 analysis and the Year 2 analysis, all patients, investigators, and site personnel will remain blinded to treatment assignments.

The trial design allows for the opportunity to efficiently submit data for regulatory review following demonstration of efficacy after Year 1 while continuing to collect data through Year 2. A limitation of releasing results of the Year 1 analyses prior to all patients completing Year 2 might include patients' perception of their treatment assignment. Note, however, that calculation of eGFR is an objective measure that is expected to be unaffected by such perceptions, and many patients will be well into their 2nd year of treatment at the time of the release of the Year 1 results. Patients and investigators will be reminded of the importance of their commitment to continue participation in the trial as part of an ongoing messaging campaign that began at the start of the trial. To minimize dropouts the sponsor has a patient retention plan in place, which includes an extended access trial (402-C-1803; EAGLE) with open-label treatment for eligible patients completing the 402-C-1603 (CARDINAL) trial.

